1.0 TRIAL SUMMARY

Abbreviated Title	Adjuvant cisplatin-chemoradiotherapy (CRT) followed by pembrolizumab in esophageal squamous cell carcinoma (ESCC) after preoperative CRT and surgery
Trial Phase	II
Clinical Indication	Locally advanced ESCC patients receiving preoperative chemoradiotherapy at high risk of recurrence (closed or involved resection margin or extranodal invasion of involved lymph nodes or ypN2-3)
Trial Type	Interventional
Type of control	N/A
Route of administration	Intravenous (IV)
Trial Blinding	Unblind
Treatment Groups	Cisplatin-CRT followed by Pembrolizumab
Number of trial subjects	Approximately 26 subjects will be enrolled
Estimated enrollment period	24 months
Estimated duration of trial	The trial will require approximately 60 months from the time the first subject signs the informed consent until the last subject's last study-related phone call or visit.
Duration of Participation	
Subjects need to sign the informed consent form to be enrolled into this trial.After a screening phase up to 28 days, each subject will receive adjuvant weekly cisplatin -CRT (cisplatin, 30mg/m²/week x 2; radiotherapy, 180-200 cGy/fraction x 10-13) followed by pembrolizumab (200mg/3 weeks x 18) (approx. a total of 56 weeks).Treatment will continue until the completion of the planned cisplatin-CRT plus 18 cycles of pembrolizumab, or until recurrent disease, unacceptable adverse events, intercurrent illness that prevents further administration of treatment, investigator's decision to withdraw the subject, subject withdrawal of consent, pregnancy of the subject, noncompliance with trial treatment, or administrative reasons requiring cessation of treatment.To detect the tumor recurrence, all patients will be evaluated by pertinent evaluation and imaging studies every 4 cycles of pembrolizumab during treatment phase, then every 3 months for post-treatment year-1 to year-2, and every 6 months for post-treatment year-3 and year-4.Subjects who discontinue for reasons other than recurrent disease will have post-treatment follow-up visits for monitoring disease status as if they were still on treatment until recurrent disease, initiating a non-study cancer treatment, withdrawing consent from study participation, or becoming lost to follow-up.All subjects will be followed (e.g., by telephone or visit) for overall survival until death, withdrawal of consent from study participation, or the end of the study, whichever comes first. After the end of study treatment, each subject will be followed for 30 days for adverse event monitoring. Serious adverse events will be

	collected for 90 days after the end of treatment or for 30 days after the end of treatment if the subject initiates new anticancer therapy, whichever is earlier.
Estimated average length of treatment per patient	56 weeks

[figure not shown]
2.0 TRIAL DESIGN

2.1 Trial Design

It is a single-arm phase II trial. The target population is patients with histologically diagnosed locally advanced ESCC patients (clinically staged at least T3 and/or any N and M0 by endoscopic ultrasonography [EUS] and fludeoxyglucose-positron emission tomography [FDG-PET]) who have received preoperative cisplatin-based chemoradiotherapy (CRT) followed by surgery, and exhibit high risk of tumor recurrence. Eligible patients will receive adjuvant cisplatin-based CRT followed by pembrolizumab for 18 cycles.

The study hypothesizes that adjuvant cisplatin-based CRT followed by pembrolizumab will improve the 1-year relapse-free survival rate for these high-risk ESCC patients from 32% to 60%. With the two-sided type 1 error probability of 0.05 and type 2 error probability of 0.2, the study needs to enroll a total of 26 patients, taking another 10% of dropout rate. The duration of patient accrual is expected as 24 months. To detect the mature overall survival data, additional follow-up period of 36 months is needed.

2.2 Trial Diagram

3.0 OBJECTIVE(S) & HYPOTHESIS(ES)

3.1 Primary Objective(s) & Hypothesis(es)

In locally advanced ESCC patients who have high risk of recurrence following preoperative CRT and esophagectomy, the study will explore the efficacy of adjuvant pembrolizumab in improving their outcomes.

(1) Objective:

- a. To improve the 1-year relapse-free survival (RFS) rate, compared with historical control.

(2) Hypothesis:

- a. The addition of pembrolizumab to adjuvant cisplatin- CRT would reduce the recurrent rate of locally advanced ESCC patients who have high risk of recurrence following preoperative CRT and esophagectomy.

3.2 Secondary Objective(s) & Hypothesis(es)

The study will also explore other efficacy endpoints and safety of adjuvant pembrolizumab in locally advanced ESCC patients who have high risk of recurrence following preoperative CRT and esophagectomy.

(1) Objective:

- a. To improve the median RFS, compared with historical control.
- b. To improve the 3-year RFS rate, compared with historical control
- c. To improve the 3-year overall survival (OS) rate, compared with historical control.
- d. To improve the median OS, compared with historical control.
- e. To determine the toxicity and safety.

(2) Hypothesis:

- a. In addition to improving the 1-year RFS rate, the addition of pembrolizumab to adjuvant cisplatin- CRT would improve median RFS in locally advanced ESCC patients who have high risk of recurrence following preoperative CRT and esophagectomy.
- b. In addition to improving the 1-year RFS rate and the median RFS, the addition of pembrolizumab to adjuvant cisplatin- CRT would also improve the 3-year RFS rate in locally advanced ESCC patients who have high risk of recurrence following preoperative CRT and esophagectomy.

- c. The addition of pembrolizumab to adjuvant cisplatin- CRT would improve the OS, through reducing the recurrence rates, of locally advanced ESCC patients who have high risk of recurrence following preoperative CRT and esophagectomy.
- d. In addition to improving 3-year OS rate, the addition of pembrolizumab to adjuvant cisplatin- CRT would also improve the median OS in locally advanced ESCC patients who have high risk of recurrence following preoperative CRT and esophagectomy.
- e. The addition of pembrolizumab to adjuvant cisplatin- CRT is safe and does not result in significant toxicities in locally advanced ESCC patients who have high risk of recurrence following preoperative CRT and esophagectomy.

3.3 Exploratory Objective

The study will also explore potential biomarkers in predicting the outcomes of locally advanced ESCC patients who have high risk of recurrence following preoperative CRT and esophagectomy, and are treated with adjuvant cisplatin-CRT and pembrolizumab.

(1) Objective:

- a. To explore the ESCC tissue-based biomarkers associated with tumor recurrence.
- b. To explore the blood-based biomarkers associated with tumor recurrence

(2) Hypothesis:

- a. Certain immune biomarkers in tumor microenvironment of esophagectomy tissues following preoperative CRT would associate with the outcomes of locally advanced ESCC patients following preoperative CRT and esophagectomy at high risk of recurrence. These tissue-based biomarkers can be explored as prognostic or predictive biomarkers for locally advanced ESCC patients in the future.
 - Immunohistochemistry (IHC) of PD-L1 expression in tumor cells and in tumor-infiltrating immune cells. IHC for different lineages of tumor-infiltrating immune cells (phenotype), including activated CD8+ T cells, regulatory T cells, natural killer cells, suppressor CD4+ T cells, tumor-associated macrophages and myeloid derived suppressor cells.
 - Immune related gene expression profile (GEP) by NanoString technology
 - Immune repertoire of tumor (deep sequencing for CDR3 region of T-cell receptor [TCR]).
 - Mutation analysis of tumor (targeted genes sequencing or whole exome sequencing [WES])
- b. Certain biomarkers in peripheral blood would associate with the outcomes of locally advanced ESCC patients following preoperative CRT and esophagectomy at high risk of recurrence. These blood-based biomarkers can be explored as prognostic or predictive biomarkers for locally advanced ESCC patients in the future.

- Critical cytokines (such as interleukin (IL)-2, IL-6, IL-8, IL-9, IL-10, IL-17, IL-21, interferon-gamma, transforming growth factor-beta, etc).
- PD-L1 (enzyme-linked immunoassay for PD-L1 in serum).
- Immune repertoire of peripheral blood (deep sequencing for CDR3 region of TCR) for correlation with tumor part.
- Circulating cell-free DNA (targeted sequencing of genomic alterations of interest) for correlation with the mutation analysis of tumor.

4.0 BACKGROUND & RATIONALE

4.1 Background

Refer to the Investigator's Brochure (IB)/approved labeling for detailed background information on MK-3475.

4.1.1 Pharmaceutical and Therapeutic Background

The importance of intact immune surveillance in controlling outgrowth of neoplastic transformation has been known for decades. Accumulating evidence shows a correlation between tumor-infiltrating lymphocytes (TILs) in cancer tissue and favorable prognosis in various malignancies. In particular, the presence of CD8+ T-cells and the ratio of CD8+ effector T-cells / FoxP3+ regulatory T-cells seems to correlate with improved prognosis and long-term survival in many solid tumors.

The PD-1 receptor-ligand interaction is a major pathway hijacked by tumors to suppress immune control. The normal function of PD-1, expressed on the cell surface of activated T-cells under healthy conditions, is to down-modulate unwanted or excessive immune responses, including autoimmune reactions. PD-1 (encoded by the gene *Pdcd1*) is an Ig superfamily member related to CD28 and CTLA-4 which has been shown to negatively regulate antigen receptor signaling upon engagement of its ligands (PD-L1 and/or PD-L2). The structure of murine PD-1 has been resolved. PD-1 and family members are type I transmembrane glycoproteins containing an Ig Variable-type (V-type) domain responsible for ligand binding and a cytoplasmic tail which is responsible for the binding of signaling molecules. The cytoplasmic tail of PD-1 contains 2 tyrosine-based signaling motifs, an immunoreceptor tyrosine-based inhibition motif (ITIM) and an immunoreceptor tyrosine-based switch motif (ITSM). Following T-cell stimulation, PD-1 recruits the tyrosine phosphatases SHP-1 and SHP-2 to the ITSM motif within its cytoplasmic tail, leading to the dephosphorylation of effector molecules such as CD3 ζ , PKC θ and ZAP70 which are involved in the CD3 T-cell signaling cascade. The mechanism by which PD-1 down modulates T-cell responses is similar to, but distinct from that of CTLA-4 as both molecules regulate an overlapping set of signaling proteins. PD-1 was shown to be expressed on activated lymphocytes including peripheral CD4+ and CD8+ T-cells, B-cells, Tregs and Natural Killer cells. Expression has also been shown during thymic development on CD4-CD8- (double negative) T-cells as well as subsets of macrophages and dendritic cells. The

ligands for PD-1 (PD-L1 and PD-L2) are constitutively expressed or can be induced in a variety of cell types, including non-hematopoietic tissues as well as in various tumors. Both ligands are type I transmembrane receptors containing both IgV- and IgC-like domains in the extracellular region and contain short cytoplasmic regions with no known signaling motifs. Binding of either PD-1 ligand to PD-1 inhibits T-cell activation triggered through the T-cell receptor. PD-L1 is expressed at low levels on various non-hematopoietic tissues, most notably on vascular endothelium, whereas PD-L2 protein is only detectably expressed on antigen-presenting cells found in lymphoid tissue or chronic inflammatory environments. PD-L2 is thought to control immune T-cell activation in lymphoid organs, whereas PD-L1 serves to dampen unwarranted T-cell function in peripheral tissues. Although healthy organs express little (if any) PD-L1, a variety of cancers were demonstrated to express abundant levels of this T-cell inhibitor. PD-1 has been suggested to regulate tumor-specific T-cell expansion in subjects with melanoma (MEL). This suggests that the PD-1/PD-L1 pathway plays a critical role in tumor immune evasion and should be considered as an attractive target for therapeutic intervention.

Pembrolizumab is a potent and highly selective humanized monoclonal antibody (mAb) of the IgG4/kappa isotype designed to directly block the interaction between PD-1 and its ligands, PD-L1 and PD-L2. KeytrudaTM (pembrolizumab) has recently been approved in the United States for the treatment of patients with unresectable or metastatic melanoma and disease progression following ipilimumab and, if BRAF V600 mutation positive, a BRAF inhibitor.

4.1.2 Preclinical and Clinical Trial Data

Refer to the Investigator's Brochure for Preclinical and Clinical data.

4.2 Rationale

4.2.1 Rationale for the Trial and Selected Subject Population

Esophageal cancer is a significant malignant disease worldwide. In 2012, more than 450,000 patients were diagnosed with esophageal cancer and more than 400,000 patients died of esophageal cancer worldwide [1]. Esophageal cancer is an even more significant cancer type in Asia than other parts of the world because more than 80% of esophageal cancer patients are diagnosed from Asian countries. Squamous cell carcinoma (SCC) is the predominant histology, and accounts for >90% of esophageal cancer diagnosed in Asian countries [1,2]. In Taiwan, there were 2,372 newly diagnosed esophageal cancer patients in 2012 and the number is increasing; among them, more than 90% were squamous cell carcinoma in histology [3].

Multimodality therapy for locoregional esophageal cancer

Locoregional esophageal cancer is a potentially curable disease. In the past, patients with locoregional esophageal cancer were typically treated with either surgery or definitive chemoradiotherapy (CRT); however, only 15% to 25% of them experience long-term, disease-free survival [4–6]. Since 1990s, multimodality therapy has been actively investigated in esophageal cancer. Among different strategies to combine various types of

treatment modality, preoperative CRT followed by surgery has been most investigated by multiple randomized control trials. A meta-analysis compiling 12 randomized trials, the majority of which used cisplatin/5-FU-based CRT, found that the survival effect of preoperative CRT for resectable esophageal cancer showed the pooled hazard ratio (HR) was 0.78 (95% CI 0.70–0.88), corresponding to an absolute survival benefit at 2 years of 8.7% [7].

The most convincing data favoring preoperative CRT for locoregional esophageal cancer thus far is disclosed in the Chemoradiotherapy for Oesophageal Cancer Followed by Surgery Study (CROSS). The trial randomized 368 patients with resectable esophageal and esophago-gastric junctional (EGJ) cancer for the treatment of preoperative paclitaxel and carboplatin-CRT or surgery alone. The data demonstrated an unequivocal survival benefit of preoperative CRT in locoregional esophageal cancer and EGJ cancer: median survivals were 49.4 months in the preoperative CRT group and 24.0 months in the surgery alone (HR, 0.657; 95% CI, 0.495 to 0.871; $P = 0.003$) [8]. The survival benefit of preoperative CRT holds true in both SCC and adenocarcinoma subtypes.

Preoperative CRT followed by surgery has thus become one of the standard-of-cares for loco-regional esophageal cancer in many centers around the world including our center, the National Taiwan University Hospital, Taipei, Taiwan. Between 2000 and 2012, we conducted three prospective phase II clinical studies investigating paclitaxel and cisplatin-based regimen as preoperative CRT in patients with locally advanced esophageal cancer at National Taiwan University Hospital, Taipei, Taiwan [9–11]. The pooled analysis of 140 locally advanced ESCC patients enrolled in the 3 phase II trials showed that the median overall survival of them was 30.9 months (95% CI 21.4–40.4) and the 3-year-OS rate of them was 45.6% (95% CI 37.2–54.0) [12].

Overall, after intensive multimodality therapy such as preoperative CRT plus surgery, 40 to 50% of patients diagnosed with locally advanced esophageal cancer can enjoy long-term disease-free. On the other hand, the rest 50–60% of the locally advanced esophageal cancer patients would succumb to recurrence and metastasis of esophageal cancer.

Prognostic factors for locoregional ESCC patients treated with preoperative CRT

Several poor prognostic factors have been identified for patients with esophageal cancer receiving definitive locoregional therapy. Closed or involved resection margin (R1 resection) has been recognized as a poor prognostic factor for patients with ESCC received preoperative CRT followed by surgery [13,14]. Most treatment guidelines, including the National Comprehensive Cancer Network guidelines, suggest adjuvant radiotherapy for esophageal cancer patients having R1 resection following esophagectomy [15].

Lymph node metastasis identified in post-CRT surgical specimens has also been identified as a poor prognostic factor for locoregional cancer patients receiving preoperative CRT [16–18]. Our own analysis based on 140 ESCC patients receiving preoperative CRT also found that lymph node metastasis, especially ypN2-3, in post-CRT pathological staging was associated with inferior progression-free survival (PFS) and OS [12]. Further, we identified that extranodal invasion (ENI) of involved lymph nodes is an independent prognostic factor

associating with inferior PFS [12], a finding corroborating other reports of esophageal cancer patients who receive surgery alone [19,20].

Overall, these observations in ESCC are in line with those in head and neck squamous cell carcinoma (HNSCC), a disease which shares very similar risk factors with ESCC. The close/involved resection margin and ENI have been recognized as the most significant prognostic factors for HNSCC. Hence, HNSCC patients with these poor prognostic factors are now routinely treated with postoperative CRT [21,22].

Based on the afore-mentioned data, the local guidelines at our center thus recommend adjuvant CRT for locoregional esophageal cancer patients who have either close/involved margin or ENI of involved lymph nodes following preoperative CRT plus surgery. Nevertheless, our recent analysis indicated that despite of adjuvant CRT, the prognosis of these patients with high risk of recurrence, i.e., involved margin, positive LN with ENI, and ypN2-3, remains very poor. Their median recurrence-free survival (RFS) was 6.7 months and their 1-year RFS rate was 32.3% (subgroup analysis for [12]).

Immune checkpoint blockade holds promise as a promising therapy for ESCC

Recently, blockade of immune checkpoints, including cytotoxic T lymphocyte antigen 4 (CTLA-4) and PD-1/PD-L1, has demonstrated promising clinical activities in multiple cancer types. The clinical activity against multiple cancer types have been generally moderate, with objective tumor response rates in the range of 15~ 30%. Mutational load and neoantigen have been identified as one of the potential biomarkers for immune checkpoints blockade [23,24]. With the advance of sequencing techniques, large-scale genomic sequencing in increasing number of patients has been conducted in multiple cancer types, including ESCC. The mutational load of ESCC is more than median in many cancer types [25–29].

The expression of PD-L1/PD-L2, another one potential biomarker for PD-1/PD-L1 blockade, was found in 42% and 48%, respectively of ESCC tumors [30]. Intratumoral abundance of CD4 and CD8 T cells has also been reported as a prognostic factor in ESCC patients [31]. The preliminary anti-tumor activity of PD-1/PD-L1 immune checkpoint blockers as a single agent in advanced esophageal cancer patients who have progressed on standard systemic chemotherapy has been recently reported. The objective tumor response of pembrolizumab in ESCC patients with positive PD-L1 expression was 29% [32]. Another study using another anti-PD-1 monoclonal antibody in a group of ESCC patients (N = 65) reported a response rate of 16% [33].

Potential synergism in antitumor effect of immune checkpoint blockade and CRT

Synergism between chemotherapeutic agents and PD-1/PD-L1 immune checkpoint blockers was reported in preclinical models of various cancers. Recently, the “abscopal effect”, which refers to a rare phenomenon of tumor regression at a site distant from the primary site of radiotherapy, was reported in patients treated with radiotherapy and immune-checkpoint inhibitors [34–36].

Collectively, the combination of PD-1/PD-L1 immune checkpoint inhibitor with CRT, which is of strong rationales to be highly synergistic in antitumor effects, is a potential strategy to

improve the outcome of locally advanced ESCC patients following preoperative CRT plus surgery at high risk of recurrence.

4.2.2 Rationale for Dose Selection/Regimen of adjuvant CRT

The dose of adjuvant radiotherapy will be 18-26 Gy given in 10-13 fractions dependent on the dose of preoperative radiotherapy. The study will enroll subjects who have been treated with preoperative CRT with radiation dose of 40-45 Gy given in 20-25 fractions per our institutional treatment standards. As a result, this radiation dose has been selected to assure that cumulated radiation dose at the loco-regional area not exceeding 66Gy, a dose range which is generally accepted as a safe and definitive RT for locoregional esophageal cancer.

The chemotherapy to be administered is weekly cisplatin (30 mg/m²) given concurrently with radiation. The rationales of using weekly cisplatin include: (1) cisplatin-based CRT has been established as a standard postoperative adjuvant therapy for patients with high-risk head and neck squamous cell carcinoma (HNSCC) [37-39], a disease that shares very similar risk factors and genetic alterations with ESCC; (2) although high-dose (100 mg/m²), once-every-3-weeks cisplatin-CRT is the standard approach, it results in severe acute toxicity in more than three quarters of HNSCC patients; (3) weekly cisplatin at the dose of 30 to 40 mg/m² has been widely accepted as general clinical practice due to multiple advantages including easy administration, lesser requirement of supportive care, and lower toxicity [40]; (4) ESCC patients who have been treated with preoperative CRT followed by radical surgery are generally fragile and not fit for intensive chemotherapy such as high-dose once-every-3-weeks cisplatin.

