5.1.2 Subject Inclusion Criteria

In order to be eligible for participation in this trial, the subject must:

1. Be willing and able to provide written informed consent/assent for the trial.
2. Be ≥ 20 years of age on day of signing informed consent.
3. Be diagnosed by pathology or cytology with a locally advanced ESCC, which is clinically stage according to the TNM system of the American Joint Committee on Cancer (AJCC) Cancer Staging System (8th edition), fulfilling one of the following criteria as determined by endoscopic ultrasound, computed tomography, bronchoscopy and positron emission tomography:
 - a. T3, N0, M0;
 - b. T4a, N0, M0;
 - c. T1–4a, N1-3, M0.
4. Have been treated with preoperative cisplatin-based CRT followed by esophagectomy with lymph node dissection for the locally advanced ESCC (defined by above criteria).
5. Have a performance status of 0 or 1 on the ECOG Performance Scale.
6. Exhibit at least one risk factor of tumor recurrence in the post-CRT surgical tissues:
 - a. Close (≤ 1 mm) or involved margin;
 - b. Residual tumor cells in lymph nodes with ENI.
 - c. ypN2-3
7. Demonstrate adequate organ function as defined in
8. Table 1, all screening labs should be performed within 10 days of treatment initiation.

Table 1 Adequate Organ Function Laboratory Values

System	Laboratory Value
Hematological	

Absolute neutrophil count (ANC)	≥1,500 /mcL
Platelets	≥100,000 / mcL
Hemoglobin	≥9 g/dL without transfusion or EPO dependency (within 7 days of assessment)
Renal	
Serum creatinine OR Measured or calculated ^a creatinine clearance (GFR can also be used in place of creatinine or CrCl)	≤1.5 X upper limit of normal (ULN) OR ≥60 mL/min for subject with creatinine levels > 1.5 X institutional ULN
Hepatic	
Serum total bilirubin	≤ 1.5 X ULN
AST (SGOT) and ALT (SGPT)	≤ 2.5 X ULN
Albumin	≥2.5 mg/dL
Coagulation	
International Normalized Ratio (INR) or Prothrombin Time (PT)	≤1.5 X ULN unless subject is receiving anticoagulant therapy as long as PT or PTT is within therapeutic range of intended use of anticoagulants
Activated Partial Thromboplastin Time (aPTT)	≤1.5 X ULN unless subject is receiving anticoagulant therapy as long as PT or PTT is within therapeutic range of intended use of anticoagulants

^aCreatinine clearance should be calculated per institutional standard.

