5.2 Trial Treatments

The treatment to be used in this trial is outlined below in Table 2.

Table 2 Trial Treatment

Drug or radiotherapy	Dose/Potency	Dose Frequency	Route of Administration	Regimen/Treatment Period	Use
Cisplatin	30 mg/m ²	QW	IV infusion	Day 1 of each week for 2 weeks, starting within 8 weeks after esophagectomy.	Adjuvant CRT
Radiotherapy	180-200 cGy	QD (Monday to Friday)		Total 10-13 fractions	Adjuvant CRT
Pembrolizumab	200 mg	Q3W	IV infusion	Day 1 of each 3 week cycle for 18 cycles, starting within 4 weeks after completing adjuvant cisplatin-CRT	Experimental

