5.2.1 Dose Selection/Modification

5.2.1.1 Dose Selection

The rationale for selection of doses to be used in this trial is provided in Section 4.0 – Background and Rationale.

Details on preparation and administration of pembrolizumab (MK-3475) are provided in the Pharmacy Manual.

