5.2.2 Timing of Dose Administration

5.2.2.1 Cisplatin-CRT:

- a. Cisplatin-CRT is to be started within 8-12 weeks after esophagectomy, when the patient recovers well from the operation.
- b. Cisplatin 30 mg/m², IV infusion for 60~ 120 min, weekly, for 2 weeks.
 - i. Sufficient hydration will be given at the discretion of the investigator.
 - ii. Anti-emetics such as 5-HT3 antagonists, aprepitant, steroid, and metoclopramide will be given at the discretion of the investigator.
- c. Radiotherapy: (intensity modulated radiotherapy) 180-200 cGy/fraction, once daily, 5 days a week, for a total of 10-13 fractions.
 - i. Radiotherapy will be administered by megavoltage linear accelerators (\geq 6 MV photon) using multiple fields (\geq 2) technique.
 - ii. Planning CT (CT simulation) must be done for isodose distribution and evaluation of dose-volume histogram.
 - iii. The target volumes of radiation should encompass the tumor volume (both primary esophageal tumor and metastatic lymphadenopathy) with adequate margins covering subclinical disease (including submucosal, mediastinal, and/or supraclavicular or celiac lymphatics) and treatment variability (including setup errors, breathing, and organ motion). Gross tumor volume (GTV) is defined as the volume of all visible esophageal tumor and involved lymphadenopathy using all available imaging studies including CT scan, EUS, and 18F-FDG-PET scan. The clinical target volume (CTV) is defined as the

GTV plus areas considered at significant risk of microscopic disease including a 0.5-1.0cm circumferential margin and 3-4 cm longitudinal margin.

- iv. Radiation will be delivered with intensity modulated radiotherapy technique, with a daily fraction size of 180-200 cGy, 5 days a week.

5.2.2.2 Pembrolizumab:

- a. Pembrolizumab is to be started within 4 weeks after completing last dose of CRT, when the patient recovers well from the CRT.
- b. Pembrolizumab should be administered on Day 1 of each cycle after all procedures/assessments have been completed as detailed on the Trial Flow Chart (Section 6.0). Trial treatment may be administered up to 3 days before or after the scheduled Day 1 of each cycle due to administrative reasons.
- c. Pembrolizumab will be administered on an outpatient basis.

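### Does the treatment section allow a cumulative radiation dose above the 66 Gy limit stated in the rationale?

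*Combined protocol and SAP*

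**What the plan says.** Section 4.2.2 makes three linked statements about radiotherapy.

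- The adjuvant dose: "The dose of adjuvant radiotherapy will be 18-26 Gy given in 10-13 fractions dependent on the dose of preoperative radiotherapy".
- The prior treatment of the enrolled patients: "preoperative CRT with radiation dose of 40-45 Gy given in 20-25 fractions", under the centre's own standards.
- The purpose of the choice: "to assure that cumulated radiation dose at the loco-regional area not exceeding 66Gy".

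Three other places state the regimen without the dependence or the limit: the trial summary in Section 1.0 ("radiotherapy, 180-200 cGy/fraction x 10-13) followed by pembrolizumab"), Table 2 in 5.2 ("Total 10-13 fractions", at 180-200 cGy) and 5.2.2.1 ("180-200 cGy/fraction, once daily, 5 days a week, for a total of 10-13 fractions").

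Inclusion criterion 4 in 5.1.2 describes the earlier treatment as "Have been treated with preoperative cisplatin-based CRT followed by esophagectomy with lymph node dissection for the locally advanced ESCC" and gives no radiation dose. The exclusion criteria in 5.1.3 give none either.

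The link between the treatment section and the rationale is in 5.2.1.1: "The rationale for selection of doses to be used in this trial is provided in Section 4.0".

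**The concern.** A cumulative-dose limit that the protocol uses to call its radiotherapy safe appears only in the rationale. Someone prescribing from Table 2 and 5.2.2.1, or checking entry against 5.1, sees the full range of 10-13 fractions and not the condition that narrows it. The top of the adjuvant range meets the limit exactly when added to the lowest preoperative dose. With higher preoperative doses, some courses that fit Table 2 go over 66 Gy. If the treatment section were the only governing text, a patient could be treated in line with it and still receive more than the protocol intends.

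**Working it through.** **Inputs.** Adjuvant fractions n = 10 to 13 (4.2.2, Table 2, 5.2.2.1). Fraction size f = 1.8 to 2.0 Gy (Table 2, 5.2.2.1). Preoperative dose P = 40 to 45 Gy and cumulative limit 66 Gy (4.2.2). The two doses are summed in full at the loco-regional area, as 4.2.2 implies; the preoperative fields are not described.

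**The plan's own figures.** The adjuvant range runs from 10 x 1.8 = 18.0 Gy to 13 x 2.0 = 26.0 Gy, which reproduces the stated 18-26 Gy. The lowest preoperative dose plus the highest adjuvant dose is 40 + 26 = 66 Gy, which reproduces the limit.

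**Totals.** Total = P + n x f. The highest P that stays within the limit is 66 - n x f.

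| n | f (Gy) | Adjuvant (Gy) | Highest P within 66 Gy | Total at P = 40 | Total at P = 45 |
|---|---|---|---|---|---|
| 10 | 1.8 | 18.0 | 48.0 | 58.0 | 63.0 |
| 11 | 1.8 | 19.8 | 46.2 | 59.8 | 64.8 |
| 12 | 1.8 | 21.6 | 44.4 | 61.6 | 66.6 |
| 13 | 1.8 | 23.4 | 42.6 | 63.4 | 68.4 |
| 10 | 2.0 | 20.0 | 46.0 | 60.0 | 65.0 |
| 11 | 2.0 | 22.0 | 44.0 | 62.0 | 67.0 |
| 12 | 2.0 | 24.0 | 42.0 | 64.0 | 69.0 |
| 13 | 2.0 | 26.0 | 40.0 | 66.0 | 71.0 |

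At 40 Gy none of the eight combinations exceeds 66 Gy. At 45 Gy five of the eight do, by up to 71.0 - 66.0 = 5.0 Gy. The unconditional range therefore does pass the limit for part of the preoperative range.

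**Can the statements all hold together?** The room left by the limit is 66 - P, which runs from 66 - 45 = 21.0 Gy to 66 - 40 = 26.0 Gy. The listed courses start at 18.0 Gy, and 10 fractions give at most 20.0 Gy, so at every P from 40 to 45 Gy at least one listed course fits. Section 4.2.2 is therefore consistent with itself and with the ranges in Section 5. The dependence on preoperative dose is what selects within the range, and subtraction gives the bound without a separate table.

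**Which text governs?** Section 4.2.2 states what the dose will be; it is not only background. Section 5.2.1.1, on dose selection, directs the reader to Section 4.0. Under 10.3 the signing investigator undertakes to follow the protocol, with no section excepted. A 45 + 26 Gy course fits Table 2 in isolation but departs from 4.2.2, so the protocol as a whole does not permit it.

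**What is known about each patient?** Section 7.1.1.5.2 requires review of prior radiation, so the preoperative dose is available at entry. Section 5.2.2.1 requires a planning CT with isodose and dose-volume evaluation for each course. Section 8.2.1 plans enrolment at one centre, and 4.2.2 says that centre's standards set the preoperative dose.

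**The case for a change.** The strongest case for a change is that a safety condition should stand where treatment is prescribed and entry is checked. The pointer in 5.2.1.1 promises a rationale and does not announce a limit. The review of prior radiation is tied to no cumulative figure, the planning requirement states none, and Table 3.2 holds radiotherapy only for toxicity or clinical conditions. The excess does not need an extreme pairing: after 45 Gy, even the smallest fraction size gives 66.6 Gy with 12 fractions and 68.4 Gy with 13. Because 5.1.2 omits the 40-45 Gy range, no specific criterion stops entry at a higher dose, and above 48 Gy even the smallest listed course (18 Gy) would pass the limit.

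The factual part of this stands. The condition is stated once, and none of the other controls restates it. Exclusion 12 in 5.1.3, which lets the investigator exclude a patient because of prior therapy, is discretionary and carries no dose.

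The inference that the plan allows such courses does not stand. It requires reading Table 2 as if 4.2.2 did not exist. Entry above 45 Gy would likewise contradict what 4.2.2 says about who is enrolled. Repeating the condition in Section 5 would be tidier, but it would add no requirement that the protocol does not already contain.

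**Conclusion.** The concern does not call for a change. The arithmetic behind it is right: Table 2 and 5.2.2.1 read alone would fit totals from 58 to 71 Gy over the 40-45 Gy preoperative range, up to 5 Gy above the stated limit. The protocol read as a whole excludes the part above 66 Gy, its figures agree from section to section, and a team following 4.2.2 stays within the limit at every preoperative dose in the range. What remains is a point of placement.

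This rests on reading 4.2.2 as binding, which its wording and 10.3 support, and on summing the two doses in full. The documents do not say how many patients received each preoperative dose, so the number for whom the limit would narrow the choice cannot be given. Neither the 1-year recurrence-free survival endpoint, the sample size of 24 raised to 26, nor the Kaplan-Meier analysis uses the radiation dose. No view is taken here on which dose or limit is clinically right.
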